7.5 Packaging and Labeling

Lyophilized drug powder is stored in 13.5 mL borosilicate glass (Type 1) bottles (Forma Vitrum AG, Hungary). Lyophilization stoppers (Helvoet Pharma, Belgium) composed of two-leg brombutyl rubber are sealed with aluminum Snap Caps and polypropylene discs (Helvoet Pharma, Belgium).

7.6 Conditions for Storage and Use

The study product is to be stored at 2°C to 8°C (36°F to 46°F) before reconstitution.

7.7 Method of Assigning Subjects to Treatment Groups

Not applicable.

7.8 Dispensing, Compliance, and Accountability

The Sponsor will provide drug accountability forms to assist the pharmacist in maintaining current and accurate inventory records covering receipt, dispensing, and the return of investigational drug supplies. When a shipment is received, the pharmacist will verify the quantities received and return the acknowledgment to the study monitor or designee. The pharmacist investigational drug accountability record includes the identification of the person to whom the drug is dispensed, the quantity and the date of dispensing and any returned or unused drug. This record is in addition to any drug accountability information recorded on the CRF. These records will be readily available for inspection by a monitor or Sponsor audits and are open to regulatory authority inspection at any time.

7.9 Prior and Concomitant Therapy

Medications having the potential to interfere with the evaluation of efficacy are excluded throughout the trial.

The following medications are strictly prohibited during the study:

- Zavesca® (miglustat)
- Ceredase® (algucerase)
- Cerezyme® (imiglucerase)
- Vpriv® (velaglucerase alfa)
- Cerdelga® (eliglustat)

The following medications are allowed and expected during the study:

- Treatments for hypersensitivity, anaphylaxis, or anaphylactoid reactions, e.g., epinephrine, norepinephrine, glucagon, albuterol
- Treatments for anemia, e.g., iron, folic acid, vitamin B₁₂
- Treatments for bone disease, e.g., bisphosphonates
- Analgesics, e.g., nonsteroidal anti-inflammatory drugs (note: aspirin may be contraindicated due to its effects on platelets and risk for bleeding)

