8. EFFICACY AND SAFETY ASSESSMENTS

8.1 Efficacy Variables

Spleen and liver volumes will be measured by MRI using a standardized protocol (see [Appendix 14.4](#)). Hemoglobin and platelet counts will be measured locally by standard laboratory procedures, and biomarkers will be analyzed at a central laboratory

Primary efficacy variable is:

- Percent change in spleen volume (expressed in MN) from baseline to Month 12

Secondary efficacy variables are:

- Percent change in liver volume (expressed in MN) from baseline to Month 12
- Percent change in hemoglobin from baseline to Months 3, 6, 9, and 12
- Percent change in platelet count from baseline to Months 3, 6, 9, and 12
- Percent change in Lyso-Gb1 from baseline to Months 3, 6, 9, and 12
- Percent change in Chitotriosidase from baseline to Months 3, 6, 9, and 12

Other efficacy variables are:

- Change in height SDS from baseline to Months 3, 6, 9, and 12
- Change in weight SDS from baseline to Months 3, 6, 9, and 12
- Change in Tanner Stage from baseline to Month 12
- Change in bone age (by X-ray of left hand and wrist) from baseline to Month 12

- Change in bone mineral density (DEXA) from baseline to Month 12
- Change in mSST from screening Month 6 and 12

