6.2.2. Sensitivity/Supplementary Analysis

There are no sensitivity and supplementary analyses planned for these endpoints.

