6.6.4. Concomitant Medications and Nondrug Treatments

The concomitant medication(s) and non-drug treatment(s) will be provided in the listings.

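### Protocol 7.9 bars drugs that could interfere with efficacy yet permits anemia treatment, and the single-arm hemoglobin analysis has no supplementary look at its effect

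*Protocol*

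**What the plan says.** Protocol 7.9 opens with a general rule: "Medications having the potential to interfere with the evaluation of efficacy are excluded throughout the trial". It names five Gaucher drugs as prohibited. It then gives a second list under the words "The following medications are allowed and expected during the study", which includes "Treatments for anemia, e.g., iron, folic acid, vitamin B₁₂" and "Treatments for bone disease, e.g., bisphosphonates".

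Protocol 8.1 makes "Percent change in hemoglobin from baseline to Months 3, 6, 9, and 12" a secondary efficacy variable, and the Month 12 change in bone mineral density an other efficacy variable. Protocol 6.2 explains that there is no control group.

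The SAP handles hemoglobin as follows:

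- SAP 2.1.2 and 6.2.1 use a treatment-policy strategy. The intercurrent events named are discontinuation of treatment and of study, followed by an open-ended 'etc'; all data collected afterwards are included.
- SAP 5.1 and 5.2.2 apply the exact two-sided Wilcoxon signed rank test to the Month 12 percent change. Appendix 4 shows that secondary endpoints are tested against zero.
- SAP 6.2.2: "There are no sensitivity and supplementary analyses planned for these endpoints". SAP 6.5 plans no subset analysis.
- SAP 6.6.4: "The concomitant medication(s) and non-drug treatment(s) will be provided in the listings". No analysis uses these data.

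Bone density is summarized descriptively (SAP 6.3).

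**The concern.** Anemia treatment acts on hemoglobin and bisphosphonates act on bone density, and both measures are efficacy variables. On its face, 7.9 therefore excludes and expects the same drugs.

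In a randomized trial, background co-treatment would tend to fall on both arms. Here the only comparison is with the subject's own baseline, so the planned test cannot separate a rise due to iron, folic acid, vitamin B12 or transfusion from one due to taliglucerase alfa. Protocol 4.4 gives an objective evaluation of hematologic effects as part of the study's aim, so the reading of the hemoglobin result is at stake.

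**Working it through.** **1. The plan's own figure.** The only power statement (Protocol 10.1) concerns spleen volume. For nine subjects and a two-sided sign test that rejects at 8 or more, or 1 or fewer, responders:

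- significance level = 2 × (9 + 1)/512 = 0.0391 (stated as 0.04)
- power at a responder rate of 0.91 = 9 × 0.91⁸ × 0.09 + 0.91⁹ = 0.809 (stated as 80.9%)

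Both reproduce, and co-treatment for anemia does not touch them. The documents give no power for hemoglobin.

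**2. What limits co-treatment effects.** Exclusion 5 (Protocol 6.3.2) keeps out untreated iron, folic acid or B12 deficiency. Screening is at Day -50 ± 10 (Protocol 9.2.1) and the hemoglobin baseline is Day 1 (SAP 3.4), so a supplement already running at screening has about 40 to 60 days to act before baseline. Neither point covers treatment started or changed after screening. Protocol 9.2.3 mentions transfusions given at the medical center, possibly a slip for infusions. No section prohibits transfusion or gives it an analysis rule.

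**3. Inputs for an illustration.**

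- True drug effect on hemoglobin: zero (assumption).
- n = 9 (Protocol 10.1).
- Gain in a co-treated subject: 1.5 g/dL (assumption) on a baseline of 11.1 g/dL, the pediatric 60 units/kg median in Protocol Appendix 1, section 14.1. 1.5/11.1 = 13.5%.
- SD of percent change: the only hemoglobin-change SD in the documents is 1.4 g/dL on a baseline of 11.4 g/dL, in adult Type 1 patients at 60 units/kg (Appendix 1, Table 4). 1.4/11.4 = 12.3%. SDs of 6% and 8% are assumptions, used to show the range.
- Number co-treated: 0 to 4 of 9 (assumption).

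**4. Calculation.** Normal percent changes were simulated, with 13.5 added for each co-treated subject, and the exact signed rank test applied (200,000 runs per cell). At n = 9 a significant rise needs a positive rank sum of at least 40, where the two-sided p is 0.0391; by chance alone this happens in 0.0391/2 = 2.0% of trials.

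| Co-treated of 9 | SD 12.3% | SD 8% | SD 6% |
|---|---|---|---|
| 0 | 2.0% | 2.0% | 1.9% |
| 1 | 3.3% | 3.6% | 3.9% |
| 2 | 5.3% | 6.7% | 7.4% |
| 3 | 8.6% | 12.2% | 14.1% |
| 4 | 13.8% | 21.2% | 26.1% |

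With three co-treated subjects the typical median change is +3.4% to +4.2%.

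**5. Why carrying a value forward is a poor remedy.** If anemia treatment starts before the Month 3 sample, the last earlier value may be the baseline itself, giving a change of zero. SAP 5.2.2 drops zeros. Four such subjects leave 9 - 4 = 5, and the smallest two-sided exact p at n = 5 is 2/2⁵ = 0.0625, so significance is impossible. For treatment started before Day 1, the last earlier value predates the baseline.

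**The case against.** The strongest reply is that the SAP does have a rule. Treatment policy includes all data whatever happens, and with at most 15 subjects the listings let a reader find every co-treated case. The efficacy decision in SAP 5.1 rests on spleen volume, and hemoglobin is one of five secondary tests without multiplicity adjustment. Exclusion 5 and the interval before Day 1 also remove part of the problem. All of this stands, and it is why the main analysis should stay. It does not answer the point: without a control arm, including the data leaves any co-treatment effect inside the reported change, and a listing does not show how far the median moves.

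Two stronger readings are tempting.

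- **Co-treatment could supply the whole hemoglobin signal.** A reader might infer this because Protocol 4.3.3 reports no meaningful hemoglobin change in two Type 3 patients. That study had 6 patients on 30 units/kg and 5 on 60. Its Type 1 patients were split 4 and 5 (Appendix 1, section 6.1), so the Type 3 patients were 6 - 4 = 2 on 30 units/kg and 5 - 5 = 0 on 60. The present trial uses 60. Protocol 4.3.5 also reports a 4.9% hemoglobin gain at 36 months in a treatment-naïve Type 3 patient. No section gives a rate of co-treatment.
- **Bone density is credited to the drug in the same way.** It is descriptive only, and DEXA is limited to children aged 9 and above (SAP 3.3.3). There is no test or decision to distort.

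**Conclusion.** The concern holds in limited form. The opening rule of 7.9 and its permitted list conflict and must be reconciled. In the planned hemoglobin test, a rise from anemia treatment started or changed around or after baseline, or from transfusion if given, would be reported within the drug effect, and no planned analysis would show its size.

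Under the stated assumptions, the chance of a significant rise with no drug effect goes from 2% to 3-7% with one or two co-treated subjects, 9-14% with three and 14-26% with four. The low end of the ranges for three and four uses the only SD in the documents, which comes from adult Type 1 patients. The size of the gain and the number co-treated have no source in the documents, so these figures show sensitivity and are not a forecast. The primary endpoint and its power are unaffected. The change is worth making because it is cheap, but the trial's main conclusion does not depend on it.

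**What to change.** - **Protocol 7.9:** reconcile the opening rule with the permitted list. This review does not say which drugs should be allowed.
- **SAP 6.2.2:** keep the main hemoglobin analysis and add one supplementary analysis at Month 12. Report the median percent change and the individual values with and without subjects who started or changed anemia treatment between screening and Month 12, or who were transfused within an interval fixed before database lock. Do not carry forward an earlier value. Interpret the result mainly by the estimate, since the reduced n may make significance impossible.
- **SAP 6.3:** flag bisphosphonate users in the descriptive bone density output.

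The cost is SAP text and one extra run. Protocol 9.2 already records medications at every visit; transfusions would have to be identifiable in the non-drug treatment data that SAP 6.6.4 lists. The downside is fewer subjects and low precision in the supplementary analysis.

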8. EFFICACY AND SAFETY ASSESSMENTS

8.1 Efficacy Variables

Spleen and liver volumes will be measured by MRI using a standardized protocol (see [Appendix 14.4](#)). Hemoglobin and platelet counts will be measured locally by standard laboratory procedures, and biomarkers will be analyzed at a central laboratory

Primary efficacy variable is:

- Percent change in spleen volume (expressed in MN) from baseline to Month 12

Secondary efficacy variables are:

- Percent change in liver volume (expressed in MN) from baseline to Month 12
- Percent change in hemoglobin from baseline to Months 3, 6, 9, and 12
- Percent change in platelet count from baseline to Months 3, 6, 9, and 12
- Percent change in Lyso-Gb1 from baseline to Months 3, 6, 9, and 12
- Percent change in Chitotriosidase from baseline to Months 3, 6, 9, and 12

Other efficacy variables are:

- Change in height SDS from baseline to Months 3, 6, 9, and 12
- Change in weight SDS from baseline to Months 3, 6, 9, and 12
- Change in Tanner Stage from baseline to Month 12
- Change in bone age (by X-ray of left hand and wrist) from baseline to Month 12

- Change in bone mineral density (DEXA) from baseline to Month 12
- Change in mSST from screening Month 6 and 12

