Study PB-06-005 was a multicenter (11 centers in Israel, Paraguay, and South Africa), double-blind trial in which 11 untreated pediatric patients (2 to <18 years of age) with a diagnosis of Type 1 or Type 3 GD (excluding acute neuropathic GD) were randomized to receive 30 units/kg (n=6) or 60 units/kg (n=5) of taliglucerase alfa intravenously every 2 weeks for 12 months. At the end of the study (Month 12) both treatment doses demonstrated the therapeutic efficacy of taliglucerase alfa in this pediatric population. Patients had an increase from baseline in median hemoglobin level, decrease in chitotriosidase and CCL18 levels, mean reduction in spleen and liver volumes, and mean increase in platelet count, height and weight, and bone age. Additionally, the Child Health Questionnaire scores showed that the quality of life of both the children and their parents/guardians improved after 12 months of taliglucerase alfa treatment. The efficacy results and the observed safety profile in these pediatric patients are consistent with previous data of taliglucerase alfa from clinical trials conducted in adult patients. No new safety signals were observed in this study.

Comparison between Type 1 GD and Type 3 GD in Pediatric Patients

The 9 patients with Type 1 GD receiving either 30 units/kg or 60 units/kg of taliglucerase alfa had improvements in hemoglobin concentration of +2.1 g/dL (20.8%) and 1.6 g/dL (15.8%), respectively, from baseline to Month 12, whereas the 2 patients with Type 3 GD had no meaningful change in hemoglobin. The changes from baseline to Month 12 in liver volume, spleen volume, and platelet count in the patients with Type 3 GD were qualitatively similar, but quantitatively less than the changes observed in patients with Type 1 GD.

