10.3.4 Efficacy Analysis

Efficacy variables are listed in [Section 8.1](#).

Analysis for the primary efficacy endpoint

The primary efficacy evaluation will be the median percent change in spleen volume (expressed in MN) from baseline to Month 12 measured by MRI. For the primary efficacy endpoint, a Wilcoxon signed rank test at 2-sided significance level of 0.05 will be applied to test the null hypothesis that the median percent change from baseline to Month 12 in spleen volume MN is equal to -20%. The median percent change from baseline and the corresponding p-value will be reported.

Frequency and percentage of the responders who have the reduction greater than 20% in spleen volume MN will be provided. The 95% confidence interval for the responder rate will be provided using Clopper-Pearson method.

Analysis for the secondary efficacy endpoints

The percent change from baseline (Visit 1 or Screening) to each assessment time point will be calculated and summarized by visit with descriptive statistics (number, mean, median, standard deviation, minimum, and maximum) for spleen and liver volume (MN), hemoglobin, platelet count, chitotriosidase and Lyso-Gb1.

The Wilcoxon signed rank test will be applied for the secondary efficacy endpoints: percent change from baseline to Month 12 in liver volume MN measured by MRI, hemoglobin, platelet count, and chitotriosidase and Lyso-Gb1 separately. Though hemoglobin, platelet counts, chitotriosidase and Lyso-Gb1 will be collected at Month 3, 6 and 9 as well, no adjustment will be made for multiple comparisons, as the changes from baseline to Month 3, 6 and 9 will be descriptively summarized only.

Analysis for other efficacy variables

For change in growth and development, the height and weight will be assigned to a SDS-scores using the World Health Organization (WHO) Child Growth Standards. The Centers for Disease Control and Prevention (CDC) reference standards will be used for the age categories where the WHO reference standards are not available. Change in growth and development assessment from baseline to each visit will be summarized using descriptive statistics by visit.

Descriptive statistics will also be reported for change in Tanner Stage, bone assessment (including bone age, bone mineral density and Z-score for each bone area), and mSST from screening to Month 6, Month 12.

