3.3. Other Endpoint(s)

3.3.1. Height SDS and Weight SDS

For change in growth and development, the height and weight will be assigned to a SDS/Z-scores using the World Health Organization (WHO) Child Growth Standards. The Center for Disease Control and Prevention (CDC) reference standards will be used for the age categories where the WHO reference standards are not available.

Height and weight will be collected at Screening, Baseline, Month 3, Month 6, Month 9 and Month 12 according to the Schedule of Activities in Section 9 of the protocol.

Z-scores include height standard deviation score (SDS) by chronologic age, height SDS by bone age, weight SDS by chronologic age, weight SDS by bone age. Z-scores will be calculated by the sponsor using SAS macros following World Health Organization (WHO) reference standards. The input variable of age will be repeatedly applied using chronologic age and bone age in order to derive the above four SDS. Detailed documents on how the physical growth curves and motor milestone windows of achievement were developed as well as application tools to support implementation of the standards is publicly available at WHO website¹ for children ages 0-5 years and for children ages 5-19 years separately. Height SDS and Weight SDS should be calculated using the Statistical Analysis System (SAS) macros available at the same website.¹

There are no WHO reference standards for weight SDS for pediatric participants >10 years of age. Therefore, as an alternative, weight SDS for all pediatric participants will be also calculated using the CDC reference standards² and SAS programs.

In calculation of the percentage change from baseline for SDS, the absolute value of the baseline will be used as the denominator to address the situation where the value is negative.

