3.3.3. Bone Measurement

Bone age assessed by X-ray of left hand and wrist will be collected at Baseline and Month 12 according to the Schedule of Activities in Section 9 of the protocol.

Bone mineral density (BMD) and Z-score assessed by dual-emission X-ray absorptiometry (DEXA) for L femoral neck, total left hip, R femoral neck, total right hip, lumbar spine, cortical bone and total body will be collected at baseline and Month 12 according to the Schedule of Activities in Section 9 of the protocol. The DEXA will be done in children 9 years of age and above.

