6.3. Other Secondary Endpoints

- Estimand strategy: Treatment policy strategy for change from baseline in height SDS, weight SDS, tanner stage, bone age, BMD and Z-score for bone assessment, total score from mSST, as well as change from baseline in organ volume measured by ultrasound if available.
- Analysis set: FAS (defined in [Section 4](#)). All participants assigned to study drug and who take at least 1 complete dose of taliglucerase alfa (or partial dose if adverse events prevent completing infusion dose).
- Intercurrent events and missing data: Data after study drug discontinuation will be excluded; Missing values won't be included in calculating change from baseline and will not be imputed.
- Descriptive statistics including n, mean, SD, median, minimum, and maximum will be presented for observed continuous variables at each visit. This includes the absolute values, change from baseline and percent change from baseline in height SDS by chronologic age, height SDS by bone age, weight SDS by chronologic age, weight SDS by bone age, bone age, BMD and Z-score for bone assessment, right and left testis volume, total score from mSST, and spleen volume, spleen volume MN, liver volume, liver volume MN measured by ultrasound.

- BDM and Z-score for bone assessment will be descriptively summarized by each bone area, such as L femoral neck, total left hip, total body, etc. that listed in [Section 3.3.3](#).
- Frequency and percentage will be provided for categorical variables at each visit, such as tanner stage.

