The definition of the worst assessment for some of the biomarkers or measurements may involve other considerations. For example, the worst assessment for bone age estimation needs to be compared to the chronological age. For tanner stage and testis volume, it will be assessed at individual case though lower categorical number or lower volume usually indicates as the worse assessment. In such cases and any parameters not specified above, the definition of the worst assessment will be decided case by case and will be documented in the programming document, such as analysis datasets specification.

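### Bone age is summarised as raw and percent change over 12 months with no reference to chronological age, so in this single-arm trial a positive change does not separate lagging, normal and catch-up maturation

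*Protocol*

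**What the plan says.** Protocol 8.1 places "Change in bone age (by X-ray of left hand and wrist) from baseline to Month 12" among the other efficacy variables. Protocol 10.3.4 gives that change descriptive statistics only. SAP 2.1 names bone age within the efficacy objectives.

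SAP 6.3 sets the summary measures: "This includes the absolute values, change from baseline and percent change from baseline in height SDS by chronologic age, height SDS by bone age". The same list goes on to include bone age itself, so bone age gets a value, a change and a percent change. Appendix 1 of the SAP lists bone assessment as a summary of observed data with no analysis model.

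Bone age meets chronological age in two other places:

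- SAP 3.3.1 uses both ages to standardise height and weight: "The input variable of age will be repeatedly applied using chronologic age and bone age in order to derive the above four SDS".
- SAP Appendix 2.1, on several observations falling in one visit window, says that "the worst assessment for bone age estimation needs to be compared to the chronological age".

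Neither document defines bone age minus chronological age, a ratio of the two, a bone-age SDS or an expected 12-month advance. On timing, SAP 3.3.3 says: "Bone age assessed by X-ray of left hand and wrist will be collected at Baseline and Month 12". Height and weight are also taken at Months 3, 6 and 9. Protocol 6.2 confirms that every participant receives the study drug.

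**The concern.** Bone age is measured in years of maturation, so it rises with the calendar in any growing child. With no control group, only a comparison with elapsed time can show whether a child has gained or lost ground, and the planned summary does not make that comparison. Height and weight are put on an age-standardised scale, and bone mineral density is accompanied by its Z-score. Bone age has no such companion.

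Appendix 2.1 already accepts the principle. If the worse of two readings cannot be identified without chronological age, an improvement cannot be identified without it either. The SAP applies this only to duplicate readings.

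At stake is what this one endpoint can show. There is also a precedent for reading a raw rise favourably: Protocol 4.3.3 says that both doses showed efficacy in the earlier paediatric study and lists "mean increase in platelet count, height and weight, and bone age" among the supporting results.

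**Working it through.** The documents state no expected change, variability or power for bone age, so there is no plan figure to reproduce.

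**Inputs from the documents**
- Nominal follow-up is 52 weeks, or 364 days: 364 / 365.25 = 0.997 year.
- SAP Appendix 2.1 allows ±42 days for imaging at Month 12 and applies this to skeletal assessments. Under its inequality, elapsed time runs from 322 to 405 days, or 0.88 to 1.11 years.
- The planned number of evaluable participants is 9 (Protocol 10.1).

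**Assumptions**
- Maturation rate r of 0.5 to 1.2 bone-age years per calendar year, with 1.0 as normal.
- SD of individual change of 0.3 to 1.0 year.

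**Formulas**, with t the elapsed years:
- raw change = r × t
- change in (bone age − chronological age) = r × t − t = (r − 1) × t

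| r | Raw change in years at 322 / 364 / 405 days | Change in the gap in years at 322 / 364 / 405 days |
|---|---|---|
| 0.5 | +0.44 / +0.50 / +0.55 | −0.44 / −0.50 / −0.55 |
| 0.7 | +0.62 / +0.70 / +0.78 | −0.26 / −0.30 / −0.33 |
| 1.0 | +0.88 / +1.00 / +1.11 | 0.00 / 0.00 / 0.00 |
| 1.2 | +1.06 / +1.20 / +1.33 | +0.18 / +0.20 / +0.22 |

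Raw change is positive in every row. The change in the gap is negative for lag, zero for normal pace and positive for catch-up. At a normal rate the visit window alone moves raw change by 1.11 − 0.88 = 0.23 year and leaves the gap unchanged.

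**Percent change** at r = 1.0 and 364 days is 100 × 0.997 / baseline bone age. For baselines of 3, 6 and 12 years this gives +33%, +17% and +8%. The same normal progress differs fourfold with starting age, so a pooled figure depends on the age mix of the children enrolled.

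**Group mean**, by normal approximation, taking all 9 as growing children with paired readings and r = 0.7, with standard error = SD / √9:
- Raw mean 0.70. With SD 1.0, z = 0.70 / 0.333 = 2.09, so the chance of a positive mean is 98.2%. With SD 0.3 it is above 99.9%.
- Gap mean −0.30. With SD 1.0, z = −0.90, so the chance of a positive mean is 18.5%. With SD 0.3 it is 0.1%.

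**Skeletal maturity.** Once bone age can no longer advance, raw change is 0 and the gap changes by 0 − 1.00 = −1.00 year over the trial, for reasons unrelated to treatment. Protocol section 5 limits growth measures to children, but SAP 6.3 summarises in the full analysis set, so the adjusted measure needs its own restriction.

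**The case against.** The strongest defence is that little depends on this variable. It has no test, threshold or success criterion, and the only efficacy decision rule (SAP 5.1) concerns spleen volume. All of that stands.

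A second defence is that the information can be recovered. Absolute bone age is reported at both visits, the interval is nominally 12 months, and height and weight SDS appear by both ages. This is partly right. A careful reader can set +0.6 year against one year elapsed, and the difference between the two SDS versions reflects bone-age delay. But that view is indirect, and the percent change cannot be read this way without each child's starting value.

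Three stronger readings are tempting and are not supported:

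- A reader might infer that normal or lagging maturation will be reported as a gain. Neither document says so. The support is a background sentence about an earlier study, which also lists raw height and weight, and this trial reports those as SDS.
- A reader might infer that SDS by bone age at Months 3, 6 and 9 will be inflated by an outdated baseline bone age. SAP 6.3 uses observed data and does not impute for these endpoints, and no rule carries bone age forward. On the text those values would simply be missing. What remains is that SAP 6.3 asks for summaries at each visit although bone age is read at only two.
- A reader might extend the criticism to bone mineral density. Its Z-score is already planned for each bone area and its summaries are already descriptive, so no change is needed there.

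**Conclusion.** The point holds as a recommendation to change a descriptive endpoint. As defined, a positive bone-age change is expected with no drug effect: about +1.0 year at a normal rate, and about +0.7 year in a child who has fallen 0.3 year further behind. Percent change adds a dependence on starting bone age. The primary conclusion is unaffected.

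The sizes rest on the assumed maturation rates, and the group-mean probabilities also on the assumed SDs. The direction needs only that bone age advances with time in growing children. The adjusted measure compares each child with normal maturation, not with untreated Type 3 disease, so it would still not isolate a drug effect. It would show whether children lagged, kept pace or caught up.

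**What to change.** In SAP 6.3 and the bone-assessment row of Appendix 1:

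1. Report the change from Baseline to Month 12 in bone age minus chronological age at the X-ray date, for participants below skeletal maturity, with that limit defined in advance.
2. Keep raw bone age at each reading as a descriptive value.
3. Drop percent change in bone age.
4. State that height and weight SDS by bone age are computed only at Baseline and Month 12.

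No new data should be needed. Chronological age is already an input to the SDS calculation (SAP 3.3.1), and skeletal assessment dates are collected (SAP Appendix 2.1). The change in the gap is the bone-age change less elapsed time, so it needs only the two X-ray dates.

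The cost is SAP wording and minor programming. The downside is a bone-age figure that will look less favourable than the raw change.
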